Hospital Discharge Process: The multiple transitions within a patient's care journey from arriving at the hospital until 72 hours post-hospital discharge involving the patient/caregivers, healthcare workers, and the health system.

Patients: Women and girls over the age of 12 years admitted to a participating health facility to give birth. Once the mother has given birth, the newborn baby becomes part of the mother-infant patient dyad.

Primary Caregiver: The person primarily responsible for the care and upbringing of the infant or underage mother enrolled in the study as a maternal infant dyad.

Abstract

The first 6 weeks after birth remains a critical period of vulnerability for mother-newborn dyads. The WHO recommends at least 4 postnatal check-ups at a facility or by a community health worker in the first 6 weeks after birth. Yet this is not possible for many dyads because of overburdened health systems and scarce family resources. Personalized risk scores can help frontline healthcare providers identify high-risk mother-newborn dyads before discharge from hospital, and guide recommendations for essential postnatal care. The health of a child is closely linked to the health of its mother, so it is essential that we consider the mother and child as a dyad. Here, we aim to develop a risk predictive algorithm that integrates data about the health of the mother and newborn to identify mother-newborn dyads who are at a high-risk of dying or hospital readmission during the post-delivery, post-discharge period. This is a mixed-method study at two hospitals in Uganda. We will conduct an observational cohort study to develop and internally validate our risk score and aim to recruit 7000 mother and newborn dyads from Jinja Regional Referral Hospital and Mbarara Regional Referral Hospital. We will engage with patients, families, and health workers through direct observation, journey mapping, process mapping, and focus group discussions to identify gaps and opportunities during in-hospital, discharge, and post-discharge care for informing the development of an evidence- and risk-based bundle of interventions to improve postnatal care (PNC) for dyads. We will leverage our experience developing, validating and implementing an innovative precision public health approach for improving post-discharge care for children in Uganda following hospitalization for severe infection. Ultimately, our personalized risk score, combined with interventions that target prevention or treatment of critical causes of death or illness, will inform evidence-based recommendations for PNC, and improve health outcomes for dyads. Treating the mother and newborn as a dyad ensures that when one is sick, the other can be more closely monitored to prevent their potential decline in health.

1.0 CHAPTER ONE: Background and literature review

In 2017, 290,000 mothers died from complications of pregnancy or childbirth, and 2.5 million newborns died within the first 6 weeks of their life globally^{9,10}. Most of these deaths occurred in sub-Saharan Africa^{9,10}. Uganda has made progress in reducing their maternal mortality and under-5 mortality rates by 25% and 42%, respectively between 1995 and 2015⁴. Unfortunately, this progress in mortality reduction has not been as rapid during the postnatal period⁵.

The first six weeks following delivery bear the most significant and persistent burden of under-5 and maternal death, and severe neonatal and maternal morbidity. Efforts are currently underway to improve outcomes immediately following births at health facilities for both mothers and newborns. However, care following facility discharge presents significant challenges and accounts for a high proportion of maternal and neonatal death and morbidity. In facilities across sub-Saharan Africa, women and their newborn infants are routinely discharged from facility within 24hrs of birth⁶. Yet, 30% of mothers who die during the first 6 weeks do so after 24 hours. Thus, the postpartum period is a vulnerable time in which women are highly susceptible to infections and complications resulting from childbirth¹³. Despite this, limited studies have examined risk factors for postpartum complications specifically in LMICs where maternal mortality rate are the highest. Understanding what puts women at risk of death due to these complications is a first step to designing effective interventions during the postpartum period. This could in turn improve child outcomes, as several studies have shown maternal and child outcomes to be inextricably linked^{14, 15}. Limited resources within the health system, in the context of significant poverty, hinder good adherence to the recommended frequency of postnatal visits throughout sub-Saharan Africa, resulting in many vulnerable families not receiving lifesaving interventions. Evidence driven discharge planning and post-discharge care is a neglected aspect of facility-based management worldwide^{6,7,8}.

Currently, the World Health Organization (WHO) recommends three in-person postnatal visits for all mothers and newborn infants born at a health facility within the first six weeks of life⁶. The evidence used in formulating this recommendation is primarily based on timing of maternal and neonatal deaths and evidence surrounding the efficacy of the components of care recommended during the postnatal period. Despite this WHO recommendation, achieving any postpartum follow-up care has been challenging in many low-resourced settings. For example, in Uganda, only 57% of women received one visit with a skilled health care provider within 41 days of delivery³. There is an important opportunity to tailor recommendations for timing and frequency of follow-up to individual risk, to guide the use of scarce healthcare resources. Personalized risk scores can help frontline healthcare providers identify high-risk dyads before discharge from hospital, and guide recommendations for essential PNC. This approach facilitates safer hospital to home transitions and efficient allocation of scarce resources. Adherence to the recommended PNC visits is critical for those at higher risk.

The development of an evidence base upon which to build recommendations for the timing and intensity of postnatal care in resource-poor countries is urgently needed. This study aims to address this gap in care coverage using a precision medicine approach to postpartum follow-up. Our approach to risk stratification integrates data about the health of both the mother and newborn. This ensures that when one is sick, the other can be more closely monitored to prevent their potential decline in health. We are working to expand our innovative precision public health approach to improving post-discharge care for mother-newborn dyads. Our aim is to build a discharge risk prediction score that identifies high-risk dyads before hospital discharge. To achieve this, we will conduct an observational cohort study in 7,000 dyads discharged together after live births at JRRH and MRRH. With the data collected from this study, we will be able to develop prediction models with up to 30 candidate predictors for both maternal and newborn outcomes separately.

2.0 CHAPTER TWO: Problem statement, justification, and conceptual framework

2.1 Problem statement

Neonatal outcomes are highly correlated with the health of the mother, an example of this is shown repeatedly by poor rates of survival of infants after maternal death^{1,2}. Prediction of risk, based on the mother and infant as a pair, is a major gap in current research and yet vital to the survival of both the mom and the infant. In our prior epidemiological study of post-discharge outcomes among 3,236 dyads, we found that most readmissions were due to infectious illness and occurred early in the post-discharge period. Of the 2,926 dyads with complete follow-up data 7.1% of dyads reported at least 1 outcome. 3.6% of newborns were readmitted, 0.8% died, and 2.7% of mothers were readmitted. For readmitted newborns, the most common diagnosis was sepsis (63%), and 19% were in respiratory distress at readmission. For readmitted mothers, the most common diagnoses were surgical site infections (51%), puerperal sepsis (43%), malaria (19%), and other infections (5%). Considering the health of the mother and newborn as a dyad is an innovative and effective approach as the health of a child is closely linked to the health of its mother. A mother's morbidity or mortality affects the health of all her children – and newborns whose mothers died during the first 6 weeks have an even greater risk of dying than those whose mothers survive¹⁵. Thus, we can improve maternal and child health outcomes by identifying both mothers and babies at increased risk of mortality or serious morbidity after hospital discharge and allocating scarce resources for targeted follow-up to those most vulnerable. This allows us to not only improve health outcomes but benefits the health system with efficient use of resources.

[figure not shown]
2.2 Justification of the study

Since 2011, we have been working with partners in Uganda to develop, validate, and implement an innovative program for children aged 6 months to 5 years who have been discharged following hospitalization for Sepsis/Severe Infection. In this quality improvement program, we call Smart Discharges, healthcare workers use an individualized risk prediction score to identify children at high risk of death or complications after discharge from a hospital

following treatment for suspected severe infection. They can then use this score to guide delivery of a counseling and community-referral program. While all participants receive counselling, only high-risk, vulnerable children receive down-referrals to community health facilities. We have shown that this approach has reduced post-discharge child mortality after in-hospital treatment for serious illness by as much as 30%. Now, we are working to expand our innovative precision public health approach to improving post-discharge care for mother-newborn dyads.

Our aim is to use our findings to inform the development an evidence-based bundle of care for both the mother and newborn. This package will ensure that low-risk mother-infant pairs receive less burdensome (yet pragmatic and feasible) postpartum care, while high risk pairs receive a more extensive bundle of interventions (such as education, nutrition, healthcare interaction and community support). The Smart Discharges for Mom and Baby package will include support targeting aspects of both clinical and emotional wellbeing. Additional extensions of this work will include validation of our risk models in women who deliver at home (26.6% of births in Uganda) or suffer a stillbirth (2.4% of births in Uganda) to ensure that more women and babies can benefit from the proposed intervention³.

2.3 Conceptual framework

Our conceptual framework is clearly embodied within the concept of precision public health. Ensuring all mothers receive the recommended 3 postnatal care (PNC) visits following a facility delivery is challenging from a resource perspective. The majority of mothers survive beyond the critical first 6 weeks. However, a proportion of dyads remain vulnerable during this period. Health systems, particularly those in resource limited settings, must be able to ensure those most in need of care can appropriately receive such care. As such, our work is guided by improving our ability to identify these vulnerable dyads and then developing a scalable and sustainable approach to ensuring the intensity of care is linked to the degree of risk.

3.0 CHAPTER THREE: Research Question and Objectives

3.1 Hypothesis

Maternal and infant characteristics collected at the time of discharge following a facility delivery can predict the risk of maternal or neonatal death or need for re-admission within six weeks of birth.

3.2 Objectives

Our primary objective is to inform the development of an integrated maternal and newborn risk-based post-discharge care program. Specifically, we aim to (1) develop and internally validate clinical risk prediction models for identifying dyads at high-risk of death or hospital readmission in the 6 week post-delivery post-discharge period, and (2) identify gaps and opportunities during in-hospital, discharge, and post-discharge care to inform the future development of an evidence-and risk-based bundle of interventions to improve PNC for dyads.

4.0 CHAPTER FOUR: Methodology

4.1 Study design

This is a mixed-methods study using both quantitative and qualitative techniques to explore and map the current postnatal discharge processes in Uganda using data from two distinct hospital settings.

- **Phase I)** We will conduct an observational cohort study informed through direct observation of the mother and newborn dyad prior to facility discharge and after delivery and follow-up telephone interviews conducted at six-weeks post-discharge.
- **Phase II)** We will conduct journey mapping with a subset of dyads enrolled in the observational cohort using direct observation and follow-up telephone interviews.
- **Phase III)** We will conduct a process mapping exercise using focus group discussion methodology with select facility staff.
- **Phase IV)** We will conduct focus group discussions with a subset of mothers enrolled in the observational cohort, as well as their family members.

Table 1. Study design overview

Phase	Methods	Participants
Aim 1: develop and internally validate clinical risk prediction models		
Phase I	Direct observation and patient interviews	Mother and newborn dyads
Aim 2: identify gaps and opportunities during in-hospital, discharge, and post-discharge care		
Phase II	Patient journey mapping using direct observation and patient interviews	Mother and newborn dyads
Phase III	Process mapping exercise	Facility health workers

Phase IV	Focus group discussion	Mothers, fathers, and grandmothers
----------	------------------------	------------------------------------

4.2 Work Plan and Timeline

STUDY TIMELINE

	2021		2022				2023				2024	
	Q3	Q4	Q1	Q2	Q3	Q4	Q1	Q2	Q3	Q4	Q1	Q2
AIM 1: Develop and internally validate clinical risk prediction models for identifying dyads at high-risk of death or readmission												
Ethics approval												
Staff hiring & training												
Patient enrollment												
Patient follow-up												
Data analysis												
AIM 2: Identify gaps and opportunities during in-hospital, discharge, and post-discharge care to inform the development of an evidence- and risk-based bundle of interventions to improve postnatal care for dyads												
Ethics approval												
Journey mapping												
Focus-group discussions												
Data analysis												
Selection of intervention												
Knowledge Translation												
Manuscripts & symposia												
Stakeholder meeting												

4.3 Study Sites

Study activities will be conducted at two hospitals (Mbarara Regional Referral Hospital (MRRH) and Jinja Regional Referral Hospital (JRRH)) in Uganda in the districts of Mbarara and Jinja.

Table 2: Characteristics of the proposed study sites.

District (Region)	Hospital	Type	Location	District population	Annual deliveries
Mbarara (Western)	Mbarara Regional Referral Hospital	Public	Semi-rural	490,000	7,500
Jinja (Eastern)	Jinja Regional Referral Hospital	Public	Urban	483,000	6,000

4.4 Study Population

Phase I: Observational Cohort Study

We will recruit 7,000 mother and newborn dyads from the two participating hospitals. Based on previously observed outcome and loss to follow-up rates, we will be able to measure the prevalence of maternal and newborn hospital readmission or death within a margin of error of 1% and develop prediction models with up to 30 candidate predictors for both maternal and newborn outcomes separately with this sample size.

Inclusion:

- Women and adolescent girls aged 12 and above delivering a single or multiple babies at the study hospital during the active recruitment phase.

Exclusion:

- Inability, for whatever reason, to provide informed consent.
- Language barrier
- Mother is from a refugee camp
- Mother has no access to phone or other means for follow-up
- Mother lives outside of hospital catchment area

We will continue to follow-up with all patients enrolled in the study. This includes enrolled mothers whose baby dies after discharge as well as enrolled babies whose mothers die. In the event that the mother dies, we will follow-up with the caregiver of the baby.

Table 3. Phase I sample size

Participants:	Sample size (n=7,000)
Maternal Infant Dyads	3,500 per facility (n=7,000)

Phase II: Patient Journey Mapping

We will randomly select 100 mothers (50 per facility) from the phase I cohort of 7,000 dyads to participate in journey mapping due to intense time to capture.

Inclusion:

- Women and adolescent girls aged 12 and above delivering a single or multiple babies at the study hospital during the active recruitment phase.
- Enrolled in Phase 1.

Exclusion:

- Inability, for whatever reason, to provide informed consent.

Exclusion:

- Inability, for whatever reason, to provide informed consent.
- Language barrier
- Mother is from a refugee camp
- Mother has no access to phone or other means for follow-up
- Mother lives outside of hospital catchment area

Table 4. Phase II sample size

Participants:	Sample size (n=100)
Maternal Infant Dyads	50 per facility (n=100)

Phase III: Process Mapping

We will purposively select a sample of 6 healthcare providers and 2 hospital administrators from each of the 2 study sites for participation in a process mapping exercise based on their level of experience, availability, and consultations from site leads (Table 4).

Inclusion:

- Healthcare providers including physicians, nurses, medical students, and residents, who have been working in the maternity ward at participating health facilities for at least 2 months.
- Hospital administrators with some oversight on maternity ward operations.

Table 4. Phase III sample size

Participants:	Sample size (n=16)
Healthcare Providers	6 per facility (n=12)
Hospital Administrators	2 per facility (n=4)

Phase IV: Focus Group Discussion

We will recruit 12 adult mothers, 12 teenage mothers, 12 fathers, and 12 grandmothers (n=48) at each of the two study sites for a total sample of 96 focus group discussion (FGD) participants. FGDs for teenage mothers will be conducted separately from adult mothers. FGDs will be conducted in a private space at each of the participating facilities. We will conduct one FGD for adult primary caregivers, one FGD for teenage primary caregivers, one FGD for fathers, and one for grandmothers at each facility for a total of 7 FGDs per facility.

Inclusion:

- Mothers, fathers, and grandmothers of children who were enrolled in phase I and who were recently discharged from a participating health facility.
- Active involvement in or knowledgeable about the maternal infant dyad's peri-discharge experience.
- Have provided written informed consent.

Participants:	Sample size (n=96)
Mothers	12 per facility (n=24)
Teenage Mothers	12 per facility (n=24)
Fathers	12 per facility (n=24)
Grandmothers	12 per facility (n=24)

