4.9 Study Limitations

This study is subject to several potential limitations. First, losses to follow-up may reduce our effective sample size, thus diminishing our power to detect significance in some variables. However, our prior work in this area suggests that our losses to follow-up will be less than 5%. Furthermore, our study sample size has compensated for these potential losses to follow-up and we thus do not anticipate this to be an issue. Second, heterogeneity in outcomes may impact modelling of post-discharge events. We observed this to be a potential limitation in our prior work, in that the predictors were different between newborns and mothers, and even among mothers, between those with caesarean sections and those who delivered vaginally. To improve our probability of success, therefore, our sample size was developed to be able to model at least 3 separate outcomes. We anticipate that this will be sufficient to create a set of models which are comprehensive to capture various outcomes. Finally, With limited numbers of focus group discussions, this study may not reach thematic saturation. If this is deemed to be the case we will add additional focus groups, following a protocol amendment.

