Appendix C: Maternal Outcomes

Table 6. Maternal Causes of readmission (n=80)

Admission Diagnosis	n (%)
Surgical site infection	41 (51.2%)
Puerperal sepsis	34 (42.5%)
Malaria	15 (18.8%)
Other Infection	4 (5.0%)
Heavy Bleeding	2 (2.5%)
PPD/psychosis	2 (2.5%)
Pre-eclampsia	1 (1.2%)
Eclampsia	1 (1.2%)
HIV	1 (1.2%)
Diarrhea	1 (1.2%)
Vomiting	1 (1.2%)
Other	8 (10.0%)
Admission Symptoms	n (%)
Abdominal Pain	45 (56.2%)
Fever (<7 days)	34 (42.5%)
Abdominal tenderness when touches	32 (40.0%)
Foul smelling vaginal discharge	23 (28.8%)
Severe headache (<24 hours)	23 (28.8%)
Abnormal tiredness	12 (15.0%)
Heavy Vaginal Bleeding	7 (8.8%)
Severe headache (>24 hours)	5 (6.2%)
Changes in vision	5 (6.2%)
Vomiting	4 (5.0%)
Shortness of breath	3 (3.8%)
Fever (>7days)	2 (2.5%)
Convulsions	2 (2.5%)
Diarrhea (<14 days)	2 (2.5%)
Diarrhea (>14 days)	1 (1.2%)
Cough (>14 days)	1 (1.2%)
Cough (<14 days)	1 (1.2%)

Other	6 (7.1%)
-------	----------

Table 7. Maternal Care seeking

Care seeking (n=80 readmitted+0 deaths)	
Did she seek care after being home with her baby post-delivery n (%)	
Yes	78 (97.5%)
No	2 (2.5%)
Number of routine postpartum visits n (%)	
0	4 (5.0%)
1	33 (41.2%)
2	32 (40.0%)
≥3	11 (13.8%)
Number of days from birth to first postnatal care visit [interquartile range]	7.00 [7.00-14.00]
Number of days from discharge to readmission median [interquartile range]	5.00 [3.00-13.5]

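### Does the shared ceiling of 30 candidate predictors overstate what 7,000 dyads can support for the maternal model?

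*Combined protocol and SAP*

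**What the plan says.** Section 4.4 (Phase I) rests the size of the cohort on two claims: prevalence estimated to within 1%, and enough data to "develop prediction models with up to 30 candidate predictors for both maternal and newborn outcomes separately with this sample size". The stated basis is "Based on previously observed outcome and loss to follow-up rates". Chapter One repeats the second claim: "we will be able to develop prediction models with up to 30 candidate predictors for both maternal and newborn outcomes separately".

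The rates are in section 2.1: "3.6% of newborns were readmitted, 0.8% died, and 2.7% of mothers were readmitted". They come from 2,926 dyads with complete follow-up out of 3,236. Appendix C confirms the maternal count in the heading of its care-seeking table: "Care seeking (n=80 readmitted+0 deaths".

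On loss, section 4.9 expects that "our losses to follow-up will be less than 5" percent. The same section notes that predictors differed between newborns and mothers, "and even among mothers, between those with caesarean sections and those who delivered vaginally", and adds that "our sample size was developed to be able to model at least 3 separate outcomes". Section 4.7 lists two models, one for the mother and one for the baby. Section 4.10 names logistic regression, elastic net and support vector machines as examples of methods, with cross-validation or bootstrapping and final models of roughly 5 to 10 variables.

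No section gives an events-per-predictor rule, a shrinkage target, or an anticipated R-squared or C-statistic.

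**The concern.** One ceiling is applied to two models whose expected event counts differ by a factor of about 1.6 (4.4/2.7). Ten events per candidate is a familiar rule; it gives about 30 for newborns and only about 18 for mothers. A reader could conclude that 30 was worked out for the newborn outcome and then carried over to the mothers.

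If so, the maternal model would screen more candidates than its events can bear. Predicted risks would be too extreme, and apparent discrimination would flatter the score. The remark about three outcomes seems to add to the problem, because any split of the mothers leaves fewer events in each part. Since this sentence justifies the cohort size for Aim 1, a wrong figure would matter.

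**Working it through.** **Inputs.** N = 7,000 (section 4.4). Newborn rate 3.6% + 0.8% = 4.4%; maternal rate 2.7% (section 2.1). Loss: none; 5% (the section 4.9 bound); or 1 − 2,926/3,236 = 9.6% (section 2.1). Analysed N is therefore 7,000, 6,650 or 6,329.

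**The plan's own figures.** The companion claim can be checked. At N = 6,650, 1.96 × √(p(1−p)/N) is 0.39 percentage points for mothers and 0.49 for newborns, so the 1% margin is met. The figure of 30 cannot be reproduced, because no rule is attached to it.

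**Events per candidate** = N × rate / 30:

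| Loss | Maternal events | per candidate | Newborn events | per candidate |
|---|---|---|---|---|
| 0 | 189 | 6.3 | 308 | 10.3 |
| 5% | 180 | 6.0 | 293 | 9.8 |
| 9.6% | 171 | 5.7 | 278 | 9.3 |

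The 4.4% treats readmission and death as separate babies. The Appendix D counts of 131 or 134 out of 2,926 (4.5% or 4.6%) give 9.9 or 10.2 newborn events per candidate at 5% loss. The exact 95% interval for 80/2,926 is 2.17% to 3.39%, which gives 145 to 226 maternal events, or 4.8 to 7.5 per candidate, at 5% loss. The imbalance is real.

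**What 30 requires.** Each rule below is an assumption, evaluated at 5% loss.

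- *Ten events per candidate:* 180/10 = 18 maternal, 293/10 = 29 newborn.
- *Five events per candidate:* 180/5 = 36 maternal, 293/5 = 59 newborn.
- *Shrinkage S = 0.90:* the limit is P = N(S − 1) ln(1 − R²/S), where R² is an assumed share of the maximum, 1 − exp{2[p ln p + (1−p) ln(1−p)]}. The maximum is 0.220 for mothers and 0.303 for newborns. For mothers at 15%, R² = 0.0330 and P = 6,650 × (−0.10) × ln(1 − 0.0330/0.90) = 24.8.

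| Share of maximum R² | Maternal limit | Newborn limit |
|---|---|---|
| 10% | 16.4 | 22.8 |
| 15% | 24.8 | 34.5 |
| 20% | 33.3 | 46.3 |

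Solving for a maternal limit of exactly 30 gives a share of 17.2%, 18.1% or 19.0% at the three loss levels. At that share the newborn limit is about 42. A single rule therefore supports 30 for both models, with the maternal model the binding one.

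**Cost if performance is lower.** With 30 maternal parameters and 5% loss, solving the same formula for S gives 0.83 at 10%, 0.88 at 15% and 0.91 at 20%.

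**The case for a change.** The best argument for a change is that a ceiling without a rule cannot be checked, and that this ceiling sizes the primary aim. The 5 to 10 variables in the final models do not settle the matter, because overfitting depends on how many candidates are screened. Resampling measures optimism but adds no events. Appendix A lists many more than 30 variables, so the ceiling is a working constraint. All of that stands.

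It does not show that 30 is wrong. Across the rules above the maternal limit runs from 16 to 36, a range that includes 30. Nor does ten events per candidate identify how the authors got there: at 4.4% it gives 29.3 with 5% loss and 27.8 with 9.6% loss, and passes 30 only with no loss (30.8). At 10% of maximum R-squared the newborn model also falls short, so the gap in justification is not specific to mothers. The shrinkage formula describes unpenalised regression and does not carry over directly to elastic net or support vector machines.

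The remark in section 4.9 is a loose statement of capacity. It does not name the three outcomes, and reading it as a split of mothers by delivery mode is a guess. The documents give no event rate by mode, and the claim of 30 in section 4.4 and Chapter One covers only the maternal and newborn models. Section 4.7 fixes the output at two. No limit for split models can be derived from this.

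**Conclusion.** The observation is accurate, but it does not call for a change. No criterion is stated, and 30 candidates have about 6 maternal events each against nearly 10 for newborns. Whether 30 is too many for mothers depends on performance that nobody yet knows: under a 0.90 shrinkage target it holds for both models from about 17% to 19% of maximum R-squared upward.

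Below that, the expected loss is modest at 15% (shrinkage 0.88) and larger at 10% (0.83). The named tools fit that risk: penalisation reduces it, and resampling exposes it provided selection is repeated inside each resample, as an analyst would normally do. Because 30 is an upper limit, analysts may screen fewer once the events are counted. Cutting the maternal list now to 18 or 25 would replace the unstated rule with one chosen by the reader, and could drop a useful predictor. That is a trade-off, not a correction.

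This rests on the prior cohort's rates carrying over, loss between 0 and 9.6%, and candidates counted as single parameters. It also takes the 0.90 target and the R-squared shares as assumptions, since the plan gives none.
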